10.4 Study Populations

The Pilot and Expansion Phases will be analyzed according to safety and efficacy parameters. Similar constraints will be applied according to study phase.

- The safety population will include all patients receiving at least one dose of MM-398 or ferumoxytol. Depending upon patients receiving MM-398 and not ferumoxytol and vice versa, the safety population may be expanded in order to not dilute any adverse event rate
- The efficacy evaluable population includes all patients receiving at least one dose of MM-398.
- The pharmacodynamic evaluable population includes all efficacy evaluable patients with the following: a) pre-treatment FMX-MRI scan(s) and b) radiological scans at 8 weeks.
- The pharmacokinetic population includes patients receiving at least one dose of MM-398 and blood samples adequately collected at the predefined points.

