10.6 Efficacy Analysis

Tumor evaluation will be measured according to Response Evaluation Criteria In Solid Tumors (RECIST) version 1.1 (Cohort 1 and 2, and non-CNS disease for Cohort 3) or modified RECIST

as defined in section 7.1.6.1 (CNS disease; Cohort 3 only). Best Overall Response (BOR) is defined as the best response as recorded from the start of MM-398 until disease progression.

Objective Response Rate (ORR) is defined as the proportion of patients with a BOR characterized as either a Complete Response (CR) or Partial Response (PR) relative to the total number of evaluable patients. Exact 95% confidence intervals based on the binomial distribution will be reported.

Clinical benefit rate is defined as the proportion of patients with a BOR characterized as a CR, PR, or Stable Disease (SD) \geq 24 weeks. Proportion of patients relative to the total number of evaluable patients will be reported with exact 95% confidence intervals based on the binomial distribution.

Duration of Response (DR) is defined as the time from first documentation of response (CR or PR whichever occurs first) to the date of disease progression or to death due to any cause, whichever occurs first.

Progression-free survival (PFS) is defined as the time from first dose of MM-398 to the date of radiologic disease progression by RECIST per Investigator or death due to any cause, whichever occurs first. Rules for declaring PFS events versus censors will be described in the SAP.

A waterfall plot will be used to display BOR with maximum percent decrease in target lesion and FMX uptake value at 24 hours.

FMX uptake (ug/mL and/or %ID/kg) will be summarized as a continuous parameter. Absolute and change from baseline will be summarized. The number of target lesions decreasing, staying the same, increasing relative to FMX uptake with various thresholds will be summarized by frequency and percent according to cycle. Box and whisker plots will be displayed for FMX uptake by time point. The relationship between FMX uptake at 1-4 hours and/or 24 hours with tumor response will be evaluated using various parameters and methods. Relationships may be explored as appropriate. Additionally, informal Fisher's exact test will be used to investigate dichotomous FMX cutpoints as related to ORR. Other graphical procedures may be implemented to explore the relationship between FMX and efficacy response.

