6 ANALYSIS POPULATIONS

- **Screened population:** This population includes all patients screened (i.e. who signed the informed consent).
- **Safety population:** This population includes all patients receiving at least one dose of MM-398 or ferumoxytol. If ferumoxytol safety population is different from MM-398 safety population, safety analysis will be performed separately on both populations.

Depending upon patients receiving MM-398 and not ferumoxytol and vice versa, the safety population may be expanded in order to not dilute any adverse event rate:

- Ferumoxytol safety population: any patient receiving ferumoxytol. All analyses using this population will be based on the treatment actually received.
- MM-398 safety population: all patient receiving at least one dose of MM-398. All analysis using this population will be based on the treatment actually received.
- **Efficacy evaluable population**: This population includes all patients receiving at least one dose of MM-398. All statistical analyses of data on non-imaging related efficacy analyses will be performed using efficacy evaluable population.
- **Pharmacodynamic (PD) evaluable population**: This population includes all efficacy evaluable patients with the following: a) pre-treatment FMX-MRI scan(s) and b) radiological scans at 8 weeks. All statistical analyses of data on imaging related efficacy analyses will be performed using PD evaluable population.
- **Pharmacokinetic (PK) population**: This population includes patients receiving at least one dose of MM-398, and blood samples at the predefined timepoints adequately collected (with no major protocol deviations affecting the PK variables & with sufficient number of plasma concentrations to estimate the main PK parameters (C_{max}, AUC)). PK analysis will be documented in a separate SAP.

The term ‘All Screened Patients’ will be used to describe the set of all patients who signed informed consent, including patients who failed screening and any others who initiated screening.

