11 EFFICACY ANALYSES

11.1 Primary Efficacy Endpoints:

The efficacy endpoints will be summarized for efficacy evaluable population and PD evaluable population by using descriptive statistics.

Pilot Phase:

- **Feasibility of FMX-MRI on identifying tumor associated macrophages (TAMs):**

FMX-MRI will be conducted on day 1 before and 1-4 h after intravenous ferumoxytol (FMX) administration, then after 24 h and/or 72 h. For the quality scan of FMX-MRI, scanner type (i.e. 1.5T), impact of scan quality on analysis (i.e. adequate for evaluation, suboptimal but completed for evaluation, or inadequate for evaluation), reasons for scan suboptimal/inadequate) and scan location (i.e. Body) will be assessed.

- **Tumor Levels of Irinotecan and SN-38:**

During pilot phase, two biopsies are collected on Day 4 of the ferumoxytol phase and two biopsies are collected three days after the first dose of MM-398. Tumor levels of irinotecan and SN-38 in core biopsy will be measured after MM-398 dosing.

Expansion Phase:

- **Feasibility of Ferumoxytol (FMX) Quantitation in Tumor Lesion**

Feasibility of ferumoxytol (FMX) quantitation in tumor lesion is also assessed through the acquisition of baseline and follow-up images of sufficient quality that enable quantitative analysis to be performed.

Eligible patients should have serial FMX-MRI scans prior to and following FMX infusion as determined by their scan group. After MRI acquisition, the R2* signal is used to calculate FMX levels in plasma, tumor lesions and reference tissue by comparison to a phantom-based standard curve.

- **The Relationship Between Ferumoxytol (FMX) tumor uptake and tumor response to MM-398**

FMX-MRI will be done for various tissues and at different timepoints. Corrected FMX uptake (post-baseline value - baseline value) will be recorded by each time point and tissues. Ferumoxytol uptakes will be associated with change in tumor lesion size.

11.2 Primary Efficacy Analysis:

Pilot Phase

In patients with NSCLC, CRC, TNBC, ER/PR positive breast cancer, pancreatic cancer, ovarian cancer, gastric cancer, GEJ adenocarcinoma or head and neck cancer, who are undergoing therapy with MM-398:

- To evaluate the feasibility of delayed ferumoxytol MRI (FMX-MRI) to identify tumor associated macrophages (TAMs)

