The quality of FMX-MRI scan on impact of evaluation will be summarized descriptively by evaluation time points. For the quality scan of FMX-MRI, number of FMX-MRI scans obtained, number of scans accepted for evaluation, and scan location (i.e. Body) at each time point will be assessed. If there is more than one image data at the same timepoint for a patient, image data are averaged first before summarizing.

- To measure tumor levels of irinotecan and SN-38
Tumor levels of irinotecan and SN-38 during Pilot phase were assessed through tumor tissue biopsy. The data are summarized using descriptive statistics with n, min, max, mean 25th percentiles (Q1), 75th percentiles (Q3) and median per lesion. Tumor levels of irinotecan and SN-38 in core biopsy are reported in Merrimack Pharmaceuticals Synopsis Clinical Study Report MM-398-01-01-02, published on 18-Dec-2014 (Appendix X). No further analysis is required.

Expansion Phase

In patients with locally advanced or metastatic breast cancer:

- To further investigate the feasibility of ferumoxytol (FMX) quantitation in tumor lesions

Feasibility of ferumoxytol (FMX) quantitation in tumor lesion is assessed through the acquisition of baseline and follow-up images of sufficient quality that enable quantitative analysis to be performed. Sufficient quality is assessed by summarizing images that are adequate for evaluation, suboptimal but completed for evaluation, or inadequate for evaluation at each visit.

- To characterize the relationship between ferumoxytol (FMX) tumor uptake and tumor response to MM-398

Ferumoxytol uptakes will be associated with change in tumor lesion size. Corrected FMX results (ug/mL) from target lesion(s) at 24-hour scan is used to measure FMX tumor uptake. For the repeated scans performed at the same timepoint, the FMX tumor uptake will be averaged first before summarizing. For patient with multiple target lesions, average corrected FMX results should be used for analysis. FMX uptake will be classified as 'low tumor uptake' or 'high tumor uptake' using overall median as cutoff. Change in tumor size is used to assess tumor response to MM-398. For patient with multiple target lesions, the best change in tumor size achieved should be used. The relationship between dichotomous FMX tumor uptake classification and tumor response to MM-398 will be assessed using Fisher's exact test.

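### The Expansion Phase feasibility percentage leaves out ferumoxytol-only patients and scans that were never obtained, so neither can lower it

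*SAP*

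**What the plan says.** **Analysis sets.** SAP section 6 states: "All statistical analyses of data on imaging related efficacy analyses will be performed using PD evaluable population". Protocol 10.4 defines that set in the same way as the SAP: "The pharmacodynamic evaluable population includes all efficacy evaluable patients with the following: a) pre-treatment FMX-MRI scan(s) and b) radiological scans at 8 weeks". Efficacy evaluable means at least one dose of MM-398. SAP 11.1 then names two sets for the primary endpoints: "The efficacy endpoints will be summarized for efficacy evaluable population and PD evaluable population by using descriptive statistics". It does not say which one governs the imaging endpoints. SAP 3.1 words pharmacodynamic (PD) evaluability as a CT scan at 8 weeks, and Protocol 5.4 words it through completed FMX procedures, evaluable FMX images and the 8-week evaluation.

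**Expansion feasibility.** SAP 11.1 and 11.2 say it is "assessed through the acquisition of baseline and follow-up images of sufficient quality that enable quantitative analysis to be performed". The summary in 11.2 consists of "summarizing images that are adequate for evaluation, suboptimal but completed for evaluation, or inadequate for evaluation at each visit". For the Pilot Phase the same section asks for "number of FMX-MRI scans obtained, number of scans accepted for evaluation"; the Expansion text has no such line. SAP 7.1 summarizes categorical data on non-missing observations. Missing data are counted there but kept out of percentages.

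**FMX uptake and response.** SAP 11.2 splits 24-hour uptake at the overall median: "The relationship between dichotomous FMX tumor uptake classification and tumor response to MM-398 will be assessed using" Fisher's exact test, with change in tumor size as the response measure. Protocol 10.6 says an informal Fisher's "exact test will be used to investigate dichotomous FMX cutpoints as related to ORR".

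**The concern.** If feasibility means acquiring usable images, failing to acquire one is a failure of the endpoint. The planned summary has nowhere to record it as such.

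- A patient given ferumoxytol but no MM-398 is in neither named set. The SAP foresees such patients: section 7.6.3 sets the end of their safety period.
- A treated patient whose scheduled scan was not obtained has no image to grade, and SAP 7.1 removes that observation from the percentage. SAP 3.1 foresees patients with incomplete FMX assessments who go on to MM-398.
- Under section 6, a Day 1 to Day 2 imaging endpoint also depends on an 8-week disease scan.

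A second issue concerns the other Expansion primary objective. Under section 6, the uptake-response table leaves out treated patients who have a 24-hour FMX value but no 8-week scan. Stopping before 8 weeks can be related to outcome, so the association would come from a selected group. For ORR, by contrast, SAP 11.3.2.3 scores insufficient data as non-response.

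At stake are the two primary descriptive estimates and how they are read.

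**Working it through.** **The plan's own figures.** The documents give no feasibility rate, threshold or expected loss. The only stated probabilities are for ORR with n = 30 and true rate 0.30. The exact binomial tails are P(X ≥ 14) = 0.0401 and P(X ≥ 13) = 0.0845 (0.08447 before rounding), against 0.04 and 0.084 stated. They reproduce, but they do not bear on feasibility. Everything below uses assumed counts.

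**Feasibility at 24 hours, per patient.** Inputs: 30 Expansion patients dosed with ferumoxytol (the planned size in SAP section 4, used here as the all-dosed number). All images obtained in treated patients are taken as adequate. A loss is a patient with no usable 24-hour scan who is either ferumoxytol-only or treated with the scan not obtained. Rate = (30 − losses)/30. The 95% limits are Clopper-Pearson: lower = Beta(0.025; x, n−x+1), upper = Beta(0.975; x+1, n−x).

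| Losses | All dosed | 95% CI | As planned |
|---|---|---|---|
| 0 | 30/30 = 100% | 88.4 to 100 | 100% |
| 1 | 29/30 = 96.7% | 82.8 to 99.9 | 100% |
| 2 | 28/30 = 93.3% | 77.9 to 99.2 | 100% |
| 3 | 27/30 = 90.0% | 73.5 to 97.9 | 100% |
| 4 | 26/30 = 86.7% | 69.3 to 96.2 | 100% |

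With two losses the planned figure is 28/28 = 100% (87.7 to 100). How visible they are depends on their kind. In the efficacy evaluable set, two treated patients without the scan show as n = 28 against N = 30. Two ferumoxytol-only patients leave n = N = 28, and the loss shows only in disposition.

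**Replaced patients.** Protocol 4.2 plans up to 30 evaluable patients and 5.4 allows replacement, so the all-dosed number can exceed 30. With 30 treated patients, two lacking the scan, plus one ferumoxytol-only patient without a usable scan, the rate is 28/31 = 90.3% (74.2 to 98.0).

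**Per scan.** SAP Tables 1 and 2 imply 5×4 + 5×4 + 10×3 + 10×3 = 100 patient-timepoints. Suppose 90% of obtained images are adequate. With 0, 5, 10 or 20 scans not obtained, the planned summary reads 90.0% each time. Over scheduled scans it is 0.9×100, 0.9×95, 0.9×90 and 0.9×80 out of 100: 90.0%, 85.5%, 81.0% and 72.0%.

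**The 8-week condition alone.** Take 30 patients, 2 with inadequate images and 4 others with adequate images but no 8-week scan. The PD-evaluable rate is 24/26 = 92.3%, against 28/30 = 93.3%. This condition by itself moves little.

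**Uptake and response.** Assume 30 treated patients with a 24-hour value, 26 of them with an 8-week scan. Take 8 responders in the 26 (30.8%; the planning ORR of 29% gives 0.29×26 = 7.5), split 6/13 high and 2/13 low uptake. Odds ratio = (6×11)/(7×2) = 4.7. Now add the other 4 as non-responders and keep the PD-evaluable median cutoff:

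- 2 high and 2 low: (6×13)/(9×2) = 4.3
- all 4 low: (6×15)/(7×2) = 6.4
- all 4 high: (6×11)/(11×2) = 3.0

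The overall response rate becomes 8/30 = 26.7%.

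**The case against.** **The losses are not hidden.** SAP 7.1 counts missing data. Section 14 puts N in the column header and defines n as non-missing. SAP 7.1 lists excluded patients, and section 8 reports the numbers dosed with each drug and in each set. Table layout is left to mock shells that are not part of the documents. This stands: a reader might infer that scans not obtained disappear from the report, and the documents do not support that. What remains is that the feasibility percentage itself cannot fall, and that disposition counts patients, not scans per timepoint.

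**A ferumoxytol-only patient is not automatically a failure.** A reader might score every such patient as one. The documents do not support that either, because the Day 1 and Day 2 scans come before MM-398 and may be perfectly adequate. If one of the two patients in the main illustration had adequate scans, the rate would be 29/30 = 96.7%.

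**The response analysis follows a prespecified set.** Protocol 10.4 and SAP section 6 agree on it, and a size-change analysis needs a follow-up scan. SAP 11.1 also names the efficacy evaluable set, which has no 8-week condition, so it is not certain that these patients are dropped. Disease evaluation is every 8 weeks, however, so many of them would have no size change in either set.

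**Larger swings in the odds ratio.** If the median is recomputed after adding the four patients, two others cross it and the table can reach 4 v 4 responders (odds ratio 1.0) or 8 v 0 (infinite). A reader might take that as the effect of attrition. It is mostly the effect of re-ranking; with the cutoff kept, the range is 3.0 to 6.4.

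**No decision hangs on it.** The study has no hypothesis test, power or feasibility threshold. This is correct, and limits the consequence to the reported estimates.

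**Conclusion.** The feasibility point holds. Whichever of the two named sets governs, ferumoxytol-only patients are outside it, and scans that were not obtained stay out of the percentage. Followed as written, the SAP can overstate feasibility and cannot understate it through these two routes. Under the assumed counts, one to four losses in 30 would put the all-dosed rate at 96.7% down to 86.7% while the planned figure reads 100%. The true size is unknown because the documents give no loss rates, and it is nil if there are no losses.

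The uptake-response point is secondary. Section 6 imposes a restriction that may be related to outcome, section 11.1 leaves its application unclear, and the direction of any bias cannot be known from the documents. Balanced attrition is nearly harmless (4.7 to 4.3). Four non-responders all in one uptake group would move the odds ratio to 3.0 or 6.4.

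**What to change.** 1. In SAP 11.1 and 11.2, analyse Expansion feasibility in the Ferumoxytol safety population, restricted to the Expansion Phase, with replaced patients kept. Use the scans scheduled for each patient's scan group as the denominator. Classify each as adequate, suboptimal, inadequate or not obtained, and count the last two as failures.
2. State one analysis set for each imaging endpoint. This reconciles SAP section 6 with SAP 11.1, and brings the PD-evaluable wording in SAP 3.1 and Protocol 5.4 into line.
3. Optional: keep the PD-evaluable FMX-response analysis and report, by uptake group, how many treated patients had a 24-hour FMX value but no 8-week scan, and why. If a supplementary Fisher table is added, base it on investigator-assessed ORR (Protocol 10.6, SAP 11.3.2.3), score insufficient data as non-response, and keep the PD-evaluable median cutoff.

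The cost is SAP wording and one extra row in the feasibility table, plus a short attrition count if the third step is taken. No new data are needed. The downside is that the feasibility rate may look less favourable and, in the optional table, stops for toxicity or withdrawal would be scored as non-response.

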7 GENERAL STATISTICAL METHODS

7.1 General Methodology

Categorical/qualitative data will be summarized using the number of non-missing observations, frequency counts and percentages. All percentages will be presented as one-decimal point, unless otherwise specified. Percentages equal to 100 will be presented as 100% and percentages will not be presented for zero frequencies.

For continuous variables, descriptive statistics will include the number of non-missing observations (n), mean, standard deviation, median, minimum and maximum. Missing data will be counted but not included in percentage calculations. Where applicable, the same number of decimal places as in the raw data will be presented when reporting minimum and maximum, 1 more decimal place than in the raw data will be presented when reporting mean and median, and standard deviation.

Unless otherwise specified, patients will be counted only once in each tabular summary (e.g. each parameter & visit combination). Reported data that are excluded from tables, e.g. patients excluded from the corresponding analysis population or extraneous measurements (e.g. repeat assessments), will be included in the patient listings.

The pre-treatment period is the time from informed consent to the date of first study drug administration of ferumoxytol or MM-398 respectively. On-treatment period for ferumoxytol is defined as time from ferumoxytol treatment administration to prior to MM-398 administration or within 30 days from date of ferumoxytol termination if patient didn't receive MM-398. The on-treatment period for MM-398 is defined as time from the first administration of MM-398 to 30

days after date of MM-398 termination. Observations recorded on the same date of the first administration of study drug will be considered as on-treatment, unless otherwise indicated by collection time. The post-treatment period is the time following 30 days after the last administration of study drug.

In general, the patient listings will be sorted by phase, patient number and assessment date (and time) if applicable.

For patients who received study drug the reference start date (RFSTDT) is the date of MM-398 administration. Study day is computed as:

- (event/visit date - RFSTDT), if event/visit date < RFSTDT
- (event/visit date - RFSTDT+1), if event/visit date ≥ RFSTDT.

Tables, figures, and listings (TFLs) including intext TFLs as described in this document and in the mock shells, will be created using SAS version 9.4 or higher. Mock table, listing, and figure shells will be developed for detailed information on the layout.

